12.5. Reporting of Serious Adverse Events and Adverse Events

12.5.1. Reporting of Serious Adverse Events to Sponsor

This section describes the responsibilities of the site investigator to report serious adverse events to the sponsor. Timely reporting of adverse events is required by 21 CFR and ICH E6 guidelines.

The site investigator will report to the NIAID Medical Monitor and the Independent Medical Monitor all serious adverse events within 24 hours of becoming aware of the event, regardless of relationship or expectedness.

CONTACT INFORMATION FOR NIAID MEDICAL MONITOR:

For serious adverse events, all requested information on the AE/SAE paper CRF will be provided. However, unavailable details of the event will not delay submission of the known information. As additional details become available, the AE/SAE paper CRF will be updated and submitted.

12.5.1.1. Reporting of Unexpected Non-Serious Adverse Events

An unexpected, non-serious adverse event that is of Grade 2 severity or higher **and** study related will be recorded and reported to the NIAID Medical Monitor and the Independent Medical Monitor.

12.5.2. Reporting to Health Authority

[name] will be the sponsor of the IND and has the responsibility of reporting all AEs and SAEs to the FDA within the reporting time limits set forth by the FDA. It is [name] ultimate responsibility to report any serious adverse event to the Independent Medical Monitor at her site and to the NIAID Medical Monitor within 24 hours of becoming aware of the event. IND sponsor must report the event to the appropriate health authorities using one of these two options:

12.5.2.1. Standard Reporting (IND Annual Report)

This option applies if the AE is classified as one of the following:

- Serious, expected, suspected adverse reactions (see Section 12.2.1.1, *Suspected Adverse Reaction,* and Section 12.2.2, *Unexpected Adverse Event*).
- Serious and not a suspected adverse reaction (see Section 12.2.2, *Suspected Adverse Reaction*).
- Pregnancies

Note that all adverse events (not just those requiring 24-hour reporting) will be reported in the Annual IND Report.

12.5.2.2. Expedited Safety Reporting

• Expedited reporting is required.

This option applies if the AE is classified as one of the following:

Serious and unexpected suspected adverse reaction [SUSAR] (see Section 12.2.1.1, Suspected Adverse Reaction and Section 12.2, Unexpected Adverse Event and 21 CFR 312.32(c)(1)i

- The IND sponsor, [name], must report any suspected adverse reaction that is both serious and unexpected. The IND sponsor must report an adverse event as a suspected adverse reaction only if there is evidence to suggest a causal relationship between the study drug and the adverse event, such as:
 - A single occurrence of an event that is uncommon and known to be strongly associated with drug exposure.
 - One or more occurrences of an event that is not commonly associated with drug exposure, but is otherwise uncommon in the population exposed to the drug
- Aggregate analysis of specific serious adverse events observed in a clinical trial (such as known consequences of the underlying disease or condition under investigation or other events that commonly occur in the study population independent of drug therapy) that indicates those events occur more frequently in the drug treatment group than in a concurrent or historical control group.
- Any findings from clinical or epidemiological studies, analysis of data pooled across multiple studies, published or unpublished scientific papers, or from animal or in vitro testing that would result in a safety-related change in the protocol, informed consent, General Investigational Plan section of the IND or other aspects of the overall conduct of the trial.

SUSARs must be reported to the FDA within FDA calendar days; fatal or immediately and must be reported to the FDA within 7 calendar days. All of these must also be reported to the NIAID medical monitor within 24 hours so that s/he can report to the NIAID/DAIT DSMB within the same 15 or 7 day timeframe. The site principal investigator must report SAEs to their respective IRBs as mandated by them. The site principal investigator must report SAEs to their respective IRBs as mandated by them.

To report a SUSAR, a finalized, initial SAE case report form (**Appendix 2**) and a MedWatch 3500A form will be generated by the site Principal Investigator and must be approved by the NIAID Medical Monitor.

Any findings from studies that suggests a significant human risk

The IND sponsor, [name], shall report any findings from other epidemiological studies, analyses of adverse events within the current study or pooled analysis across clinical studies or animal or *in vitro* testing (e.g. mutagenicity, teratogenicity, carcinogenicity) that suggest a significant risk in humans exposed to the drug that would result in a safety-related change in the protocol, informed consent, investigator brochure or package insert or other aspects of the overall conduct of the study.

12.5.3. Reporting of Adverse Events to IRBs/IECs

The site investigator shall report adverse events, including expedited reports, in a timely fashion to their respective IRBs/IECs in accordance with applicable regulations and guidelines. All *Safety Reports to the FDA* shall be distributed by [name].

12.6. Pregnancy Reporting

The investigator shall be informed immediately of any pregnancy in a study subject who has initiated study treatment. A pregnant subject shall be instructed to stop taking study medication. The investigator shall counsel the subject and discuss the risks of continuing with the pregnancy and the possible effects on the fetus. Monitoring of the pregnant subject shall continue until the conclusion of the pregnancy.

The investigator shall report to the DAIT/NIAID all pregnancies within 1 business day of becoming aware of the event using the Pregnancy paper CRF. All pregnancies identified during the study shall be followed to conclusion and the outcome of each must be reported. The Pregnancy paper CRF shall be updated and submitted to the DAIT/NIAID when details about the outcome are available.

Information requested about the delivery shall include:

- o Gestational age at delivery
- Birth weight, length, and head circumference
- o Gender
- Appearance, pulse, grimace, activity, and respiration (APGAR) score at 1 minute, 5 minutes, and 24 hours after birth, if available
- Any abnormalities.

Any complication to pregnancy such as a congenital abnormality or birth defect shall be submitted as an SAE to the DAIT/NIAID using the SAE reporting procedures described above and to the FDA.

12.7. Reporting of Other Safety Information

The site investigator shall promptly notify the site IRB as well as the DAIT/NIAID when an "unanticipated problem involving risks to subjects or others" is identified, which is not otherwise reportable as an adverse event.

12.8. Review of Safety Information

12.8.1. Medical Monitor Review

The DAIT/NIAID Medical Monitor shall receive annual reports from the protocol chair compiling new and accumulating information on AEs, SAEs, and pregnancies recorded by the study site(s) on appropriate paper CRFs.

In addition, the Medical Monitor shall review and make decisions on the disposition of the SAE and pregnancy reports received by the protocol investigator (See Sections 12.5.1, *Reporting of Serious Adverse Events to Sponsor*, and 12.6, *Pregnancy Reporting*).

12.8.2. DSMB Review

12.8.2.1. Planned DSMB Reviews

The NIAID Allergy and Asthma Data and Safety Monitoring Board (DSMB) shall review safety data at least yearly during planned DSMB Data Review Meetings. Data for the planned safety reviews will include, at a minimum, a listing of all reported AEs and SAEs.

The DSMB will be informed of an Expedited Safety Report submitted to the FDA.

12.8.2.2. Ad hoc DSMB Reviews

In addition to the pre-scheduled data reviews and planned safety monitoring, the DSMB may be called upon for *ad hoc* reviews. The DSMB will review any event that potentially impacts safety at the request of the NIAID Medical Monitor. In addition, the following events will trigger an *ad hoc* comprehensive DSMB Safety Review:

- Any death that occurs in the study.
- The occurrence of the same unexpected SAE in 3 or more of the study participants who have received a study treatment.

After review of the data, the DSMB will make recommendations regarding study conduct and/or continuation.

12.8.2.2.1. Temporary Suspension of Enrollment and/or Drug Dosing for *ad hoc* DSMB Safety Review

A temporary halt in enrollment and/or drug updosing will be implemented if an *ad hoc* DSMB safety review is required per the criteria outlined in section 12.8.2.2. above.

In the event of a study halt for DSMB review, subjects in the screening phase will continue to undergo screening procedures unless the review was triggered by events related to screening.

Subjects already receiving therapy will remain on study treatment at their current tolerated dose.

Based on the outcome of the DSMB review, the consent and/or assent forms may be revised. Upon approval of these revisions by the IRB, all subjects who have previously provided informed consent for the study and are affected by the new information will be re-consented.

13.Statistical Considerations and Analytical Plan

13.1 Overview

This double blind, randomized, placebo controlled study in peanut-allergic children and adults intends to identify basic immune mechanisms that explain the effects of OIT in individuals who do or do not become clinically tolerant and to determine whether immune monitoring can predict safety and outcomes in OIT protocols.

The 120 enrolled subjects will be randomized 2.4:1.4:1. Thus, there will be three arms: (1) Arm A (60 subjects) on peanut OIT until week 104 and once meeting criteria [*i.e.* 1) assigned to OIT treatment for minimum 104 weeks, 2) reaching maintenance 13 weeks prior to DBPCFC at week 104 3) no severe reactions (Grade 3, APPENDIX 4) to home dosing from Week 92-Week 104, and/or 4) no objective reactions, (Appendix 4) at the Week 104 DBPCFC] has been assigned to avoid peanut (i.e. 600 mg oat flour). (2) Arm B (35 subjects) on peanut OIT until week 104 and once meeting criteria, has been assigned to be maintained on 300 mg peanut protein (i.e. 600 mg peanut flour). (3) Arm C (25 subjects) that is maintained on placebo (oat flour) and once meeting criteria, will receive 600 mg oat flour beginning on week 104. This will be true even if a subject in the placebo group meets criteria at week 104. This way all participants will receive approximately the same volume of flour so that the subject blinding will be easier to maintain. The decision to maintain subjects on only 300 mg peanut protein after week 104 is for ease of eating peanut for so long. This upfront randomization is performed because our statistical analysis plan is focused on intent-to-treat principles.

The primary analysis is an intent-to-treat comparison of success rates between arms A and C, where success is defined by reaching and passing the DBPCFC at both 104 weeks and 117 (or equivalent) weeks.

13.2. Endpoints

Primary Endpoint

• Proportion of peanut allergic subjects who pass a DBPCFC after the 3 month avoidance period (Week 117 or equivalent) following the end of active treatment phase.

Measurement: A DBPCFC is considered a "pass" if the subject has no clinical reactivity during the challenge (from administration of first dose through observation period lasting 2 hours after administration of the final dose).

Secondary Endpoints:

- Proportion of PA subjects who pass a DBPCFC after a 6 month avoidance period.
- Proportion of PA subjects who pass a DBPCFC after a 9 month avoidance period.
- Proportion of PA subjects who pass a DBPCFC after a 12 month avoidance period.
- Proportion of PA subjects who can successfully complete the build-up phase of peanut OIT to the highest dose (4,000 mg of peanut protein) with only mild (Objective, **APPENDIX 4**) symptoms

- Proportion of PA subjects who can successfully undergo the build-up and maintenance phases of peanut OIT with only mild symptoms.
- Comparison of the proportion of subjects in placebo, avoidance, and 300 mg peanut protein groups who are able to undergo DBPCFCs with no clinical reactivity after initiating OIT.

Measurement of Secondary Endpoints: For measurement of Bullets 1-3 and Bullet 6, see Measurement of Primary Endpoint above. Data for measurement of Bullets 4 and 5 will be collected from subject diaries, reviewed at every updosing visit attempt and DBPCFC visit conducted after successful completion of the Initial Dose Escalation Day.

13.3. Measures to Minimize Bias

This study will employ a randomized, double-blind, placebo controlled design (peanut OIT vs. placebo OIT).

13.4. Analysis Plan

13.4.1 Analysis Populations

- Intent-to-treat (ITT) sample: All subjects who are randomized will comprise the ITT sample.
- Safety sample: All enrolled subjects who receive at least one dose of OIT or placebo. Participants in the safety sample will be analyzed according to the treatment they actually received, regardless of their randomized assignment.

13.4.2 Primary Analysis of Primary Endpoint(s)/Outcome(s)

The primary analysis is an ITT comparison of success rates between arms A and C (defined in Section 13.1), where success is defined by reaching and passing the DBPCFC at Week 117 (or equivalent). An unevaluable test will be considered a failure. The analysis will be performed using the binomial test of proportions. A two-sided alpha level of 0.05 will be used. The success rate in each of the three arms will also be estimated, with 95% exact binomial confidence interval.

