3.1. Description of Study Design

A Phase 2, single-center, randomized double blind, placebo controlled study of the induction of peanut tolerance by oral immunotherapy (OIT). Our intent to treat population will be 120 subjects, ages 7-55 years, with an allergy to peanut, as determined by DBPCFC, history, clinical symptoms, and positive skin prick test (SPT). Please see Figure 1.

First, subjects will be screened (Part I, Figure 1). The 120 enrolled subjects will be randomized 2.4:1.4:1 (please see section 13). Thus, there will be three arms: (1) Arm A on peanut OIT until week 104 and once meeting criteria *[i.e. 1) on OIT treatment for minimum 104 weeks, 2) taking daily maintenance dose of 4,000 mg protein for at least 13 weeks, 3) no severe reactions (Grade 3, APPENDIX 4) to home dosing from Week 92-Week 104, and/or 4) no objective reactions, (Appendix 4) at the Week 104 DBPCFC]* has been assigned to avoid peanut (i.e. 600 mg oat flour). (2) Arm B on peanut OIT until week 104 and once meeting criteria, has been assigned to be maintained on 300 mg peanut protein (i.e. 600 mg oat flour). (3) Arm C that is maintained on placebo (oat flour) and once meeting criteria, will receive 600 mg oat flour beginning on week 104. This will be true even if a subject in the placebo group meets criteria at week 104. This way all participants will receive approximately the same volume of flour so that the subject blinding will be easier to maintain. The decision to maintain subjects on only 300 mg peanut protein after week 104 is for ease of eating peanut and to test if a lower amount of protein can still maintain desensitization. This upfront randomization is performed because our statistical analysis plan is focused on an intent to treat analysis.

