All arms will undergo an Initial Dose Escalation (IDE) Day and updosing regimen with a maintenance phase of OIT or placebo to a maximum of 4,000 mg protein daily, as peanut flour, in the OIT groups, and to a maximum of an equivalent amount of oat flour for the placebo group). (Part III, Figure 1). After maintenance is achieved, all subjects will begin performing DBPCFCs (staged so as to ensure safety) at Week 104 and every 13 weeks thereafter (Part IV, Figure 1). At Week 104, individuals that reach criteria (Part IV, Figure 1) will, based on the randomization that was done at the start of the study, either stop therapy with peanut and be switched to oat flour, or will be maintained on 300 mg peanut protein per day (Parts V, Figure 1). If subjects fail the week 104 DBPCFC they will not be given home doses. Those that fail the week 104 FC will remain in the study and return for a study completion visit at week 117 to meet the primary endpoint (will be analyzed in the intent to treat comparisons). All subjects will be evaluated every 13 weeks thereafter until the end of study.

Individuals in Arm A will be defined as "clinically tolerant" if there is no clinical reactivity at the Week 104 and Week 117 (or equivalent) DBPCFC. Clinical reactivity is defined as any objective reaction based on the Bock's Criteria (**Appendix 4**). Individuals in Arm A who meet the definition of "clinically tolerant" will continue to avoid peanut protein (i.e. continue on 600 mg per day of oat flour) as long as each subsequent DBPCFC (performed every 13 weeks until end of study) shows no clinical reactivity.

Individuals in Arm B will be defined as "desensitized" to a minimum of 300 mg per day of peanut protein if they show no clinical reactivity at DBPCFCs (week 117 (or equivalent) to end of study).

Individuals in Arm C will be defined as "natural loss of responsiveness" if they show no clinical reactivity at DBPCFCs (week 117 (or equivalent) to end of study).

We plan to identify the basic immune mechanisms which can explain the differences in the effects of OIT in individuals who do or do not become clinically tolerant and to determine whether immune monitoring can predict the safety and efficacy outcomes in peanut OIT protocols. After initial screening and enrollment, there are three phases of the study:

- Dose escalation and Build up Phase (Part III, Figure 1)
- Maintenance phase (Part IV, Figure 1)
- Tolerance and Desensitization Testing phase (Part V, Figure 1)

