3.2. Primary Endpoint

Proportion of peanut allergic subjects who pass a DBPCFC after the 3-month avoidance period (Week 117 or equivalent) following the end of active treatment phase

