13.6. Statistical Hypotheses

For the primary comparison, the following will be tested:

- Null hypothesis: The success rate (where success is passing the DBPCFC at both 104 and 117 (or equivalent) weeks) is equal in arms A (active treatment followed by 3 months of avoidance) and C (placebo).
- Alternative hypothesis: The success rate differs between arms A and C.

As a secondary comparison, the following will be tested:

- Null hypothesis: The success rate is equal in arms A and B (active treatment followed by 3 months of 300mg peanut protein treatment).
- Alternative hypothesis: The success rate differs between arms A and B.

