13.7. Sample Size Considerations

In the previous trial by Burks et al, 2013 the rate of success among subjects treated as in arm A was 0.35. Literature (Sampson, et al. 2013) suggests that the rate of success among subjects on placebo (as in arm C) is

0.05 or less. Using a binomial test of proportions with two-sided alpha level 0.05, the sample size of 60 subjects on arm A and 25 subjects on arm C yields 90% power to detect that difference (between rates of 0.35 and 0.05). According to the definition of the endpoint – passing the DBPCFC at both 104 and 117 (or equivalent) weeks – subjects who drop out of the study are included in the analysis (counted as failures). Therefore, the analysis will include all subjects randomized to arm A or arm C, and the sample size is not decreased due to drop-outs.

The following table displays the power for other possible success rates in the two arms.

		Arm C Population Success R	ate	
		0.025	0.05	0.075
Arm A	0.25	76%	59%	44%
Population	0.30	89%	77%	64%
Success	0.35	96%	90%	80%
Rate	0.40	99%	96%	91%
	0.45	100%	99%	97%

14. Identification and Access to Source Data

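### Primary success is a Week 117 pass alone in 13.4.2 and the endpoint wording, but a pass at both Weeks 104 and 117 in 13.1, 13.6 and 13.7

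*Protocol*

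**What the plan says.** Two sections describe the same intent-to-treat comparison of Arms A and C as the primary analysis.

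- **Week 117 only.** Section 13.4.2: "where success is defined by reaching and passing the DBPCFC at Week 117 (or equivalent"). Section 3.2 gives the endpoint as "Proportion of peanut allergic subjects who pass a DBPCFC after the 3-month avoidance period (Week 117 or equivalent"), and the synopsis and 13.2 agree with it.
- **Weeks 104 and 117.** Section 13.1: "success is defined by reaching and passing the DBPCFC at both 104 weeks and 117 (or equivalent) weeks". The null hypothesis in 13.6: "where success is passing the DBPCFC at both 104 and 117 (or equivalent) weeks". Section 13.7, giving the endpoint definition behind the power calculation: "passing the DBPCFC at both 104 and 117 (or equivalent) weeks". The Arm A definition of clinical tolerance in 3.1 also needs both visits.

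The cross-reference to 13.1 inside 13.4.2 attaches to the arms. It does not bring in the success rule of 13.1. The statement in 13.4.2 that an unevaluable test is a failure follows a sentence that names Week 117 only.

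**The concern.** This is the success rule of the only powered comparison. Anyone who does not pass Week 104 but passes Week 117 is a success under 13.4.2 and a failure under 13.1, 13.6 and 13.7. The primary result then depends on which section the analyst follows. The protocol fixes the rule twice, differently, so a statistical analysis plan would have to overrule one of its own protocol sections. Section 3.1 also lets research staff be unblinded once the Week 117 visits are complete, so an unresolved choice could be made with the data in view.

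**Working it through.** **1. Where the rules disagree**

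| Week 104 | Week 117 | 13.4.2, 3.2, 13.2 | 13.1, 13.6, 13.7 |
|---|---|---|---|
| pass | pass | success | success |
| pass | not pass | failure | failure |
| not pass | pass | **success** | **failure** |
| not pass | not pass | failure | failure |

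Only the third row differs, so the Week 117 rule can only add successes.

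**2. Can the third row occur?** Several passages leave it open.

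- Section 3.1: "all subjects will begin performing DBPCFCs (staged so as to ensure safety) at Week 104 and every 13 weeks thereafter".
- Section 3.1 also says that those who fail Week 104 "return for a study completion visit at week 117 to meet the primary endpoint".
- The first sentence of 8.3 on Weeks 117 to 156 gives the challenge to subjects without restriction.
- The Week 104 criteria end "and/or 4) no objective reactions, (Appendix 4) at the Week 104 DBPCFC". The connective does not make the challenge result clearly necessary, and a missed or unevaluable challenge is not expressly excluded.

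Arm C is the more exposed arm. Section 8.3 expects placebo participants to stay as sensitive as at screening, so most of the 25 should fail Week 104. If they are rechallenged, any Week 117 pass falls in the third row.

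**3. The plan's own power figure.** Inputs from 13.4.2 and 13.7: n = 60 and 25, rates 0.35 and 0.05, two-sided alpha 0.05. The test is taken as the pooled two-proportion z test.

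- Pooled rate = (60 × 0.35 + 25 × 0.05)/85 = 22.25/85 = 0.2618
- SE under the null = √[0.2618 × 0.7382 × (1/60 + 1/25)] = 0.1047
- SE under the alternative = √[0.35 × 0.65/60 + 0.05 × 0.95/25] = 0.0754
- Power = Φ[(0.30 − 1.96 × 0.1047)/0.0754] = Φ(1.26) ≈ 89.6%

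This matches the stated 90%, and all 15 cells of the 13.7 table reproduce within 0.5 point. The figure belongs to the both-visits rule.

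**4. What one reclassified participant does.** One added success moves Arm A by 1/60 = 1.7 points or Arm C by 1/25 = 4 points. Smallest Arm A count reaching p < 0.05:

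| Arm C successes (of 25) | Arm A needed (of 60) | p at that count | p with one fewer |
|---|---|---|---|
| 0 | 9 | 0.041 | 0.055 |
| 1 | 13 | 0.045 | 0.062 |
| 2 | 17 | 0.040 | 0.055 |
| 3 | 20 | 0.044 | 0.059 |

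Example with 12/60 in Arm A:

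- Arm C 0/25: z = 0.20/√[(12/85)(73/85)(1/60 + 1/25)] = 0.20/0.0829 = 2.41, p = 0.016
- Arm C 1/25: z = 0.16/√[(13/85)(72/85)(1/60 + 1/25)] = 0.16/0.0857 = 1.87, p = 0.062

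**5. How often the count lies that close.** All 61 × 26 outcomes were enumerated with binomial probabilities, taking the rates shown as the true both-visits rates. Each figure is conditional on one participant being reclassified.

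| True rates A / C | One more Arm C success removes significance | One more Arm A success creates it |
|---|---|---|
| 0.35 / 0.05 | 13.0% | 2.4% |
| 0.25 / 0.05 | 28.2% | 6.5% |

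**6. Power under Week 117 alone.** The shift in each arm is not in the protocol. Assumed additions to 0.35 (A) and 0.05 (C) give:

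- +2 points in both arms: 86.8%
- +5 points in both arms: 83.2%
- +5 points in A only: 96.3%
- +5 points in C only: 68.5%

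**The case against.** The strongest reply is that the third row is empty by design, so the Week 117 wording is only shorthand.

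- Figure 1 sends only those meeting the Week 104 criteria into the phase that holds the Week 117 challenge.
- Section 3.1 says those who fail the Week 104 challenge get no home doses, and the return visit it describes is not expressly a challenge.
- One sentence of 8.3 admits placebo participants to the later visits only if they pass the Week 104 criteria.
- The Appendix 1 footnotes tie the Week 117 challenge to meeting those criteria and call Week 117 a possible early completion visit for Week 104 reactors. The early-completion column shows no challenge mark, though the table layout may be imperfect in the text read here.
- The word *reaching* in 13.4.2 may imply having come through Week 104, and the unevaluable-test rule is worded generally.

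On size, 12/60 is well below the planned rate. Near the planned rates, 21/60 against 1/25 gives p = 0.003; adding one or two Arm C successes gives 0.011 and 0.032, both still significant. The 28% figure uses rates at which the protocol's own power is only 59%.

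Much of this stands. It supports a small number of affected participants, possibly none, and a planned-size effect would usually survive one reclassification. It does not settle the point. The unrestricted statements in 3.1 and 8.3 remain in the text, and treating the two rules as equal means choosing among conflicting passages.

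**Conclusion.** The contradiction is certain; its numerical effect is not. Two incompatible success rules are written for the primary comparison. If no one fails to pass Week 104 and then passes Week 117, they give the same result. If one Arm C participant does, the chance that this removes significance is about 13% at the planned rates and 28% at 0.25 against 0.05. For one Arm A participant, the chance that it creates significance is about 2% and 7%. These figures assume the pooled z test and exactly one reclassification, whose probability the protocol does not allow anyone to estimate. The sample size calculation is sound for the both-visits rule. The point should be fixed because it concerns the primary success rule and the correction is nearly free.

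**What to change.** In the synopsis, 3.2, 13.2 and 13.4.2, adopt the definition already used in 13.1, 13.6 and 13.7: success is an evaluable pass at both the Week 104 and the Week 117 DBPCFC, and a failed, missing or unevaluable test at either visit is a failure. Extend the unevaluable-test sentence in 13.4.2 to name both visits.

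Separately, the passages in 3.1, 8.3, Figure 1 and Appendix 1 on who is challenged at Week 117, including the *and/or* in the Week 104 criteria, must be reconciled with each other. Which clinical rule applies is for the investigators.

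The statistical change costs wording only. The sample size and the stated 90% power do not change, because 13.7 already uses this definition.
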